### **8.3.1.3 Sensitivity Analyses**

Sensitivity analyses will be performed to assess the robustness of the main estimator of the primary estimand. These sensitivity analyses will be performed with missing data imputed by the multiple imputation approach using the Markov Chain Monte Carlo (MCMC) method, a placebo-based pattern mixture model, and a tipping point method, respectively. The details of these analyses will be provided in the SAP.

CCI

The within-subject errors are assumed to be independent and identically distributed normal random variables, and are assumed to be independent of the random intercept. The details of this analysis will be provided in the SAP.

### **8.3.2 Secondary Efficacy Analyses**

Secondary efficacy endpoints include change from baseline at Week 52 in GA lesion area, the square root of GA lesion area, BCVA score, LLVA letter score, LLD in EDTRS letters at a starting distance of 4 meters, binocular reading speed (by MNRead or Radner reading charts), binocular critical print size (by MNRead or Radner reading charts), FRI composite score, and NEI VFQ-25, as well as change and percent change of CH50 from baseline at each visit.

The change from baseline will be analyzed using a linear mixed-effects model. The model includes fixed effects for treatment, visit, treatment-by-visit interaction, and the baseline outcome value as a covariate. The covariance structure for this model will be assumed to be unstructured. If the model does not converge under this assumption, then a compound symmetry covariance structure will be used. Within the framework of this model, a point estimate of the treatment group difference at Week 52 between each NGM621 group and the pooled Sham group will be provided. The corresponding two-sided 95% confidence interval and p-value for the point estimate will also be presented.

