#### 8.3.1.2 Main Estimation

The GA lesion area (at baseline, Week 24, and Week 52) will be analyzed using a random coefficients model. The model includes terms for time (continuous variable assuming linearity) and treatment-by-time interaction. The intercept and slope of time are assumed to

be random effects with a bivariate normal distribution and an unstructured (UN) covariance matrix while the treatment-by-time interaction is assumed to be a fixed effect. CCI

Within the framework

of this model, a point estimate of the treatment group difference in the regression slope between each NGM621 group and the pooled Sham group will be provided.

[figure not shown]
The corresponding two-sided 95% confidence interval and p-value for the point estimate will also be presented.

A hierarchical testing procedure will be used to control the family-wise type-I error rate associated with the tests of the two NGM621 groups (NGM621 Q4W vs pooled Sham and NGM621 Q8W vs pooled Sham). Specifically, the comparison between NGM621 Q4W and pooled Sham will be performed first. If this test is statistically significant at the 5% level, then the comparison between NGM621 Q8W and pooled Sham will be performed. If the first test is not statistically significant at the 5% level, then the comparison between NGM621 Q8W and pooled Sham will be considered exploratory.

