#### **8.6 Sample Size Determination**

Subjects will be randomized in a 2:1:2:1 ratio to receive treatment with NGM621 Q4W, Sham Q4W, NGM621 Q8W, or Sham Q8W. Subjects from the two Sham groups will be pooled in the data analysis.

A sample size of 106 subjects per treatment group (i.e., 318 subjects in total) is expected to provide approximately 90% (NGM621 Q4W vs pooled Sham) and 85% (NGM621 Q8W vs pooled Sham) power to detect a statistically significant treatment group difference in the rate of change in GA lesion area over the 52 weeks of treatment. The power is estimated based on simulations assuming a mean GA lesion area of 8 mm^2 at baseline for all subjects, a common standard deviation of 4 mm^2 for GA lesion area, a linear slope of 2 mm^2 per year for the

pooled Sham group, 1.4 mm^2 per year for NGM 621 Q4W and 1.45 mm^2 per year for NGM 621 Q8W, a within-subject correlation of 0.95, a statistical significance level of 5% (two-sided), and a 10% of subject dropout rate. These assumptions are based on published data

CCI

CCI

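### The secondary mixed model uses one baseline coefficient for all visits, which can cost some precision in the Week 52 GA-area contrast if growth depends on baseline lesion size

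*Combined protocol and SAP*

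**What the plan says.** Section 8.3.2 and the matching synopsis text analyse change from baseline with a linear mixed-effects model: "The model includes fixed effects for treatment, visit, treatment-by-visit interaction, and the baseline outcome value as a covariate". On the residual covariance: "The covariance structure for this model will be assumed to be unstructured", with compound symmetry as the fallback if the model does not converge. The output is one contrast per active arm: "a point estimate of the treatment group difference at Week 52 between each NGM621 group and the pooled Sham group will be provided".

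GA area is measured by FAF at screening (serving as baseline), Week 24 and Week 52, so two post-baseline visits share the baseline coefficient.

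The sample-size section (8.6) gives "approximately 90% (NGM621 Q4W vs pooled Sham) and 85% (NGM621 Q8W vs pooled Sham) power", assuming "a common standard deviation of 4" mm² and "a within-subject correlation of 0.95". It gives no correlation between baseline area and growth and no measurement-error SD. The primary model (8.3.1.2) has a random intercept and random slope with a free covariance, so it lets growth vary with baseline area but does not say how strongly.

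**The concern.** Growth in area accumulates. If larger lesions grow faster, baseline area predicts the change to Week 52 more strongly than the change to Week 24, by roughly 52 to 24. A single coefficient cannot fit both visits.

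Generalised least squares does not split the difference evenly. The two changes are highly correlated and the Week 24 change is less variable, so the Week 52 coefficient can receive a negative weight. The shared estimate then falls below even the Week 24 value, and the Week 52 contrast is under-adjusted.

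What is at stake is the width of the interval for a secondary endpoint that closely parallels the primary one.

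**Working it through.** **1. The plan's own figure.** Inputs from 8.6: SD 4, correlation 0.95 (taken as equal between any two visits), slopes 2, 1.4 and 1.45 mm²/yr, 106 per group, 10% dropout, two-sided 5%. Evaluable per group: 106 × 0.9 = 95.4. Visits are at t = 0, 24/52 and 1 year.
- Within-subject variance: 16 × 0.05 = 0.8. Sum of squares of t about its mean: 0.501. Slope variance per subject: 0.8/0.501 = 1.597.
- SE of the slope difference: √(2 × 1.597/95.4) = 0.183.
- Power = Φ(δ/SE − 1.96): 90.6% for δ = 0.60 and 85.2% for δ = 0.55. The stated 90% and 85% reproduce.

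**2. Cost of the shared coefficient under that structure.** The covariance of baseline with change is 16 × 0.95 − 16 = −0.8 at either visit, so the coefficient needed is −0.8/16 = −0.05 at both. The shared coefficient is also −0.05. Week 52 residual variance is 1.60 − 16 × 0.05² = 1.56, and SE = √(2 × 1.56/95.4) = 0.181 with or without the interaction. The loss is zero.

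**3. Cost if growth varies between subjects and depends on baseline.** Assumptions not in the documents: growth SD 1.2 mm²/yr, measurement SD σ, and correlation r between true baseline area and growth. Observed baseline variance is kept at 16. With s the subject's growth rate and e the measurement error, C24 = (24/52)s + e24 − e0 and C52 = s + e52 − e0.

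Worked case, r = 0.3 and σ = 0.3:
- Cov(true baseline, s) = 0.3 × √15.91 × 1.2 = 1.436.
- Coefficient needed at Week 24: (0.4615 × 1.436 − 0.09)/16 = 0.036. At Week 52: (1.436 − 0.09)/16 = 0.084.
- Residual variances given baseline: 0.466 (Week 24) and 1.507 (Week 52); covariance 0.706.
- GLS weights are proportional to 1.507 − 0.706 = 0.801 for Week 24 and 0.466 − 0.706 = −0.240 for Week 52, which scale to +1.43 and −0.43.
- Shared coefficient: 1.43 × 0.036 − 0.43 × 0.084 ≈ 0.015, against 0.084 needed.
- Variance ratio at Week 52: 1 + (0.084 − 0.015)² × 16/1.507 = 1.05, so the SE is 2.5% larger. A 5% variance cost is about 5 of 106 subjects per group.
- Share of baseline's variance reduction kept: 1 − (0.069/0.084)² ≈ 33%.
- Power for 0.60: SE 0.178 with the interaction and 0.182 without, or about 92% against 91%.

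Increase in the Week 52 SE over the assumed range:

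| σ | r = 0.2 | r = 0.3 | r = 0.4 | r = 0.5 | adjustment kept |
|---|---|---|---|---|---|
| 0.2 | 1.5% | 3.5% | 6.4% | 10.6% | 16–24% |
| 0.3 | 1.1% | 2.5% | 4.6% | 7.4% | 27–41% |
| 0.5 | 0.5% | 1.2% | 2.1% | 3.4% | 34–60% |

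Simulation at σ = 0.3 (3,000 trials per setting, 95 per group) gave 1.8%, 2.3%, 4.7% and 7.2%.

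**4. A second parameterisation.** Here the Week 52 change variance is held at the 1.6 implied by 8.6, and the share due to measurement error is varied. At r = 0 the loss is zero.
- At r = 0.3, the SE is 0.4%, 2.7% and 4.2% larger for error shares of 50%, 10% and 2%.
- At r = 0.5, the figures are 1.1%, 7.9% and 13.3%.
- Simulated SEs, shared against by-visit: 0.177 and 0.173 (r = 0.3, 10% error); 0.180 and 0.160 (r = 0.5, 2% error).

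All figures in steps 2 to 4 use complete data on the evaluable number; partial follow-up was not modelled.

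**The case against.** The strongest reply is that the loss rests on inputs the documents do not supply. Under the covariance that reproduces the plan's power, it is exactly zero. That stands, and the point must be conditional. But compound symmetry has no between-subject variation in slope, whereas the primary model allows it. Zero loss there follows from a simplified sizing assumption and does not show that one coefficient is adequate.

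A reader might infer more than the documents support:
- **That the Week 52 contrast is in effect unadjusted.** At r = 0.3 and σ = 0.3 about a third of the adjustment is kept, and at σ = 0.5 about half. The negative Week 52 weight also depends on measurement error. With change variance held at 1.6 and r = 0.3, it is −0.42 at σ = 0.3, −0.01 at σ = 0.5 and +0.20 at σ = 0.63.
- **That chance imbalance in lesion size would distort the result.** A one-SE imbalance is 4 × √(2/106) = 0.55 mm². At r = 0.3 and σ = 0.3, the uncorrected part moves the contrast by 0.55 × 0.069 = 0.04 mm², against a planned difference of 0.60. Randomisation rules out bias.
- **That every secondary endpoint is affected.** Only GA area was computed. Nothing is shown for square-root area, visual function, the questionnaires or CH50.

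Section 8 also promises a separate SAP that overrides the protocol and might contain the term. It is not part of the documents reviewed.

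**Conclusion.** The point holds as a conditional, modest matter of efficiency. As written, one baseline coefficient serves both visits while only Week 52 is contrasted. If growth depends on baseline area, part of the Week 52 adjustment is lost, and most of it when measurement error is small.

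With growth SD 1.2 and measurement SD 0.2 to 0.5, the cost is about 0.5 to 3.5% of SE at correlations of 0.2 to 0.3 and about 2 to 11% at 0.4 to 0.5. It goes slightly beyond those ranges only when measurement error is a very small share of the change variance (4.2% and 13.3% at a 2% share). It is nil under the planning structure of 8.6 or at zero correlation. The model as specified is valid: the Week 52 estimate is unbiased and the primary random coefficients test is unaffected.

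**What to change.** Before unmasking, add a baseline-by-visit interaction to the model in 8.3.2, the synopsis and the SAP for Week 52 change in GA area. With two post-baseline visits this costs one extra parameter, which is immaterial at about 95 evaluable subjects per group; under the planning structure the simulated SEs were 0.180 without the term and 0.181 with it. Pre-specifying it prevents the choice from looking data-driven.

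The same term may be used for other endpoints with few post-baseline visits, but the gain there was not computed. BCVA is different: it has 14 post-baseline visits to Week 52 in the Q4W arms, so the term would add 13 parameters to an unstructured model that already carries a convergence fallback. Decide that case separately. If a common coefficient is kept for GA area, the plan should say why.

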CCI																	
Dosing (please see Table 5)																	

OU = both eyes; SE = study eye; X= Required

 Females of childbearing potential only; Serum pregnancy test to be conducted at screening. Urine pregnancy test to be conducted on Day 1 and Week 52 visit. If pregnancy is suspected, a serum pregnancy test may be conducted.

 For the screening visit only, it is allowable to draw blood in the order of assessments as listed in the table OR the blood draw can occur right before the FA assessment to allow for a single needle stick.

 Columns shaded gray indicate that adverse event reporting will be by telephone (📞) for non-visit months (Weeks 12, 20, 28, 36, and 44) for subjects in the Q8W arm only.

 The patient-reported outcome (PRO) measures (NEI VFQ-25 and FRI Index) will be administered by the masked site staff (except for the VA examiner) prior to any other visit assessments being performed.

 Reference [Section 7.3.12.1](#) and the pharmacy manual for details.

 A FA and SD-OCT should be performed if the development of CNV is suspected in study eye. The central reading center must confirm this finding before any intervention is initiated. See [Section 7.3.15](#) for details.

 After randomization, if a patient misses a study visit when FAF images were scheduled to be taken, the images should be taken at the next scheduled visit.

 Microperimetry is optional and applies to select sites.

 PK, anti-drug antibody and neutralizing antibody samples will be collected at Day 1 pre-dose, at Week 1 post-dose (PK collection only), Week 4 post-dose, Weeks 8, 16, 24, 40, 48 pre-dose, and on Weeks 52 and 56.

 For subjects who discontinue early from the study, the EOT visit assessments should be performed after a minimum of 28 days has elapsed from the last administered dose. See [Section 6.7](#) for details.

 For subjects who consented to the optional sample collection.

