### 7.3.7 BCVA/LLVA

Best corrected visual acuity will be measured by trained and certified personnel at the study sites. The visual acuity (VA) examiner must be masked to each subject's study (treated) eye and treatment arm (study drug vs. Sham) assignment. VA will be measured at the intervals specified in [Table 4](#) and [Table 5](#).

The name and certification number of the vision examiner should be documented in the subject's visual acuity (VA) worksheet (provided by the Sponsor or designee) at each visit. Retroilluminated ETDRS charts are used in this trial. Refraction should be conducted prior to visual acuity testing to obtain best-corrected vision. Best-corrected visual acuity at a starting distance of 4 meters is measured at all office-based study visits using standard charts, lighting, and procedures. The low luminance visual acuity (LLVA) has the same requirements as the best corrected visual acuity; however, the low luminance visual acuity will be measured by placing a 2.0-log-unit neutral density filter over the best correction for that eye and having the participant read the normally illuminated Early Treatment Diabetic Retinopathy Study chart.

A description of the VA assessment is detailed in the Study Procedure Manual or equivalent.

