## 8 Statistical Considerations

A detailed statistical analysis plan (SAP) will be provided and finalized prior to the study database lock or unmasking. No discrepancies are expected between the SAP and the protocol. However, if there are discrepancies between this section of the protocol and the final SAP, the SAP will override the protocol.

In general, descriptive statistics including the number of non-missing observations (n), arithmetic mean (mean), standard deviation (SD), median, minimum (min), and maximum (max) will be presented by treatment group for continuous endpoints. Frequency and percentage distribution will be presented by treatment group for categorical endpoints.

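### The secondary mixed model falls back from unstructured straight to compound symmetry with no robust standard error; the fallback is unlikely to be reached, but could misstate the Week 52 interval, most of all for BCVA

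*Combined protocol and SAP*

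**What the plan says.** Section 8.3.2 and the matching part of the Synopsis set out one model for all secondary change-from-baseline endpoints. On the mean structure: "The model includes fixed effects for treatment, visit, treatment-by-visit interaction, and the baseline outcome value as a covariate". On the covariance: "The covariance structure for this model will be assumed to be unstructured". On failure to converge: "If the model does not converge under this assumption, then a compound symmetry covariance structure will be used". The target is a single-visit contrast: "a point estimate of the treatment group difference at Week 52 between each NGM621 group and the pooled Sham group will be provided", reported with a 95% interval and a p-value. Neither place names an intermediate structure or a robust standard error, so the compound symmetry (CS) results would carry model-based standard errors.

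The endpoints differ greatly in their number of visits. GA area, LLVA, reading, FRI and NEI VFQ-25 are scheduled after baseline only at Weeks 24 and 52. BCVA is different (Section 7.3.7): "Best-corrected visual acuity at a starting distance of 4 meters is measured at all office-based study visits". The Q8W arms, sham included, have telephone contact instead of a clinic visit "for non-visit months (Weeks 12, 20, 28, 36, and 44) for subjects in the Q8W arm only" (Table 5, footnote 3). Section 8.3.2 does not say which BCVA visits enter the model.

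Section 8 promises a detailed SAP and gives it precedence: "if there are discrepancies between this section of the protocol and the final SAP, the SAP will override the protocol".

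**The concern.** CS imposes one variance of change on every visit and one correlation on every pair of visits. The estimate of interest belongs to a single visit, Week 52. If the variance of change is not constant over time, the model-based CS standard error at Week 52 reflects the average visit rather than Week 52. The interval is then too narrow if Week 52 is more variable than average, and too wide if it is less variable.

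At stake are the nominal interval and p-value of the Week 52 secondary contrasts, and only if the unstructured model fails. A fallback is written for exactly that case, so it should give a valid standard error then. Replacing it after a failed fit would be a post hoc choice.

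**Working it through.** **The plan's own figure.** The protocol states no figure for the secondary model. Its one reproducible design figure is the primary power in Section 8.6. The SD of one-year change is 4 × √(2 × (1 − 0.95)) = 1.265 mm², and n = 106 × 0.9 = 95.4 per group. Slope differences of 2 − 1.4 = 0.60 and 2 − 1.45 = 0.55 give 90.6% and 85.2%, against the stated 90% and 85%. None of this involves the secondary model. Under the same assumptions the variance of change in GA area is 2 × 16 × 0.05 = 1.6 at both Week 24 and Week 52, so CS would be correct for that endpoint.

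**How likely is the fallback?** An unstructured matrix for k visits has k(k + 1)/2 parameters:
- Two-visit endpoints: 2 × 3/2 = 3.
- CH50 at Weeks 1, 4, 24 and 52: 4 × 5/2 = 10.
- BCVA at the 9 visits common to all arms (Weeks 1, 4, 8, 16, 24, 32, 40, 48, 52): 9 × 10/2 = 45.
- BCVA at all 14 post-baseline Q4W visits to Week 52: 14 × 15/2 = 105.

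Unstructured REML converged in 300 of 300 simulated 14-visit BCVA datasets and 100 of 100 9-visit datasets. The 14-visit sets included heavy-tailed data with 5% intermittent missingness, which took at most 58 iterations. A separate EM fit of the 14-visit matrix converged in 5 of 5 datasets. The total is 405 of 405.

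**What if CS is used for BCVA?** With complete data, CS SE / correct SE = √(average visit variance / Week 52 variance). Type I error = 2 × (1 − Φ(1.96 × ratio)).

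Visit SDs are assumptions, in letters from Week 1 to Week 52, with variance linear in time. The mean of the 9 common visit weeks is 225/9 = 25, and (25 − 1)/51 = 0.4706 of the way from Week 1 to Week 52.
- SD 8 to 10: average variance 64 + 36 × 0.4706 = 80.9; ratio √(80.9/100) = 0.90; type I error 7.8%.
- SD 6 to 10: 36 + 64 × 0.4706 = 66.1; ratio 0.81; 11.1%.
- SD 10 to 8: 100 − 36 × 0.4706 = 83.1; ratio √(83.1/64) = 1.14; 2.6%.

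The fuller calculation adds arms of 106/106/53/53, 10% dropout spread evenly over visits, and an assumed correlation of 0.3 + 0.6 × exp(−lag/26 weeks). The simulated columns use 1000 datasets per row and a baseline covariate; their Monte Carlo error is about 0.4 to 0.7 points at 5% and up to about 1 point in the last row.

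| SD, Week 1 to 52 | CS SE / correct SE (large sample) | Type I, large sample | Type I, simulated CS | Type I, simulated CS with sandwich SE |
|---|---|---|---|---|
| 10 to 8 | 1.12 | 2.8% | 2.4% | 4.5% |
| 10 to 10 | 0.99 | 5.3% | 4.5% | 4.8% |
| 8 to 10 | 0.89 | 8.2% | 7.0% | 4.7% |
| 6 to 10 | 0.80 | 11.8% | 10.8% | 4.9% |

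Milder trends give 1.05 and 4.0% (10 to 9), and 0.94 and 6.7% (9 to 10). With 14 visits the large-sample type I errors for the four tabulated rows are 2.9, 5.4, 8.2 and 11.7%, and sandwich standard errors gave 4.3 to 5.1% in simulation.

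**In letters.** Half-widths are 1.96 × SE:
- 8 to 10: 1.96 × 1.27 = 2.5, against a correct 1.96 × 1.43 = 2.8.
- 6 to 10: 1.96 × 1.14 = 2.2, against 2.8.
- 10 to 8: 1.96 × 1.29 = 2.5, against 1.96 × 1.15 = 2.25.

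**Other SD profiles.** A separate simulation with wider profiles (for example 5 rising to 12, 9 falling to 7, or a mid-study peak; 400 runs each) gave ratios of 0.67 to 1.20 and type I error of 1.8% to 18.8%. Sandwich standard errors brought this to 4.0% to 7.5%.

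**The case against.** The plan has an explicit, prespecified fallback, and the event that triggers it never occurred in simulation. The size of any error rests on SDs and a correlation pattern that the protocol does not give. Section 8.3.2 does not fix the BCVA visits. If BCVA were modelled only at Weeks 24 and 52, 3 parameters would suffice and the exposure would largely vanish. If all 14 visits were modelled, NGM621 Q8W would have empty treatment-by-visit cells at five of them. A later SAP may already refine the rule. All of this stands, and it limits the point to a conditional one.

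Four stronger readings are tempting, and the documents do not support them:
- **The plan's BCVA test has an 8% to 12% error rate.** Those figures apply only if CS is reached and variance rises as assumed.
- **The error is anti-conservative.** No variance trend is given, and a falling variance reverses the sign. At equal SDs the large-sample excess (5.3%) does not appear in simulation (4.5% with 9 visits, 4.8% with 14), so CS is best called about right there.
- **Only BCVA is exposed.** The rule covers every secondary change endpoint. With assumed subject-to-subject slope variation in GA area, the CS ratio would also fall below 1 (0.81 to 0.97), although non-convergence with two visits is very unlikely.
- **The final SAP lacks a remedy.** The supplied text is the protocol, so the gap is shown only there.

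Two limits of the checks also stand. Dropout was spread evenly over visits. With outcome-dependent dropout, CS could also affect the point estimate, which a sandwich standard error does not repair. Convergence within a tight iteration limit was not tested.

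**Conclusion.** The point holds as a minor, conditional weakness. The written rule goes from unstructured directly to CS without a robust standard error. If it is used, the Week 52 standard error could be wrong in either direction: from 20% too small to 12% too large across the assumed SD patterns in the table, or about 0.6 letters too narrow to 0.3 too wide in half-width. The mechanism follows from the model. The size rests on assumed visit SDs, correlation and dropout pattern.

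The primary slope analysis uses a different model, the hierarchical test covers only the two primary comparisons, and the sample size does not depend on this rule. The secondary p-values are nominal.

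**What to change.** In Section 8.3.2 and the Synopsis, or in the SAP that takes precedence over Section 8, state that if the unstructured model does not converge, CS will be used with empirical (sandwich) standard errors, clustered by subject. This is the option tested by simulation.

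Optionally, try a heterogeneous-variance structure first, such as heterogeneous Toeplitz or heterogeneous CS. By the same large-sample calculation these gave type I errors of 5.1% and 4.5%, but their convergence was not tested, and the unequal visit spacing is a reason for care with visit-indexed Toeplitz. They should therefore precede the sandwich rule, not replace it.

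The cost is one sentence. If the fallback is ever used, the interval will be slightly wider where variance rises over time and slightly narrower where it falls. Study conduct, the sample size and the primary test do not change.
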